10.2 Analysis of Adverse Events

All adverse events will be coded using the most current version of the Medical Dictionary for Regulatory Activities (MedDRA). Adverse events will be summarized by primary MedDRA system organ class (SOC) and preferred term (PT). Subjects reporting more than one adverse event for a given PT will be counted only once for that term. Subjects reporting more than one adverse event within an SOC will be counted only once for the SOC total. Subjects reporting more than one adverse event will be counted only once in the overall adverse event total. For summaries by SOC and PT, the SOCs will be presented in alphabetical order and the PTs will be presented in alphabetical order within each SOC.

A treatment-emergent adverse event (TEAE) is defined as any adverse event with onset during the treatment period or within 30 days of the end of the treatment period:

- For the OMT group this includes all adverse events with onset after the day of randomization and within 30 days following the last visit.
- For LCIG treatment subjects who have all study tubes removed after their last study drug infusion, this includes all adverse events with onset on or after the date of the initial tube placement procedure and no more than 30 days

> following the last study tube removal, or no more than 30 days following the last LCIG infusion if there is no final device removal in the study.

[figure not shown]
10.2.1 Adverse Event Overview

The number and percentage of subjects experiencing one or more adverse events in the following adverse event categories during the 12-week Treatment Period will be summarized.

- Any TEAE
- Any TEAE that was rated by the investigator as having a reasonable possibility of relationship to levodopa-carbidopa intestinal gel
- Any severe TEAE
- Any serious TEAE
- Any TEAE that led to discontinuation of study drug
- Any treatment emergent GI event (as defined in Section 10.2.3)
- Any TEAE other than a GI event (as defined in Section 10.2.3)
- A fatal TEAE
- All deaths

The number and percentage of subjects experiencing one or more adverse events in the following adverse event categories during the Transition Period will be summarized.

- Any TEAE
- Any TEAE that was rated by the investigator as having a reasonable possibility of relationship to levodopa-carbidopa intestinal gel
- Any severe TEAE
- Any serious TEAE
- Any TEAE that led to discontinuation of study drug
- Any treatment emergent GI event (as defined in Section 10.2.3)
- Any TEAE other than a GI event (as defined in Section 10.2.3)

- A fatal TEAE
- All deaths

Serious adverse events with onset during the Screening Period for all subjects screened, adverse events and serious adverse events with onset after day of randomization and before day of initial device placement for the LCIG group, as well as adverse events during the transition period for LCIG subjects continuing LCIG commercial treatment will also be summarized.

10.2.2 Adverse Event Incidence

The number and percentage of subjects experiencing one or more adverse events in the following adverse event categories during the 12-week Treatment Period will be summarized for each treatment group and for overall subjects by primary SOC and PT for overall treatment interval.

- Any TEAE
- Any serious TEAE
- Any TEAE that led to discontinuation of study drug

The percentage of subjects in the LCIG group and in the OMT group will be compared using Fisher's exact test. Only *P* values ≤ 0.100 when rounded to three digits will be presented.

The number and percentage of subjects experiencing one or more adverse events in the following adverse event categories during the Transition Period will be summarized for LCIG subjects who enter the Transition Period by primary SOC and PT.

[figure not shown]
- Any TEAE
- Any serious TEAE
- Any TEAE that led to discontinuation of study drug

The number and percentage of subjects experiencing one or more TEAEs during the 12-week Treatment Period will also be summarized for each treatment group and for overall subjects by maximum severity category (mild, moderate, severe, or unknown) and primary SOC and PT for overall treatment interval. Subjects reporting more than one TEAE for a given PT will be counted only once for that term in the most severe category reported. If a subject has an adverse event with unknown severity, then the subject will be counted in the severity category of "unknown," even if the subject has another occurrence of the same event with a severity present. The only exception is if the subject has another occurrence of the same adverse event with the most extreme severity -"Severe." In this case, the subject will be counted under the "Severe" category.

The number and percentage of subjects experiencing one or more TEAEs during the 12-week Treatment Period will also be summarized for each treatment group and for overall subjects by maximum relationship category (reasonable possibility, no reasonable possibility, or unknown), as assessed by the investigator, and primary SOC and PT for overall treatment interval. Subjects reporting more than one TEAE for a given PT will be counted only once for that term in the most related category reported. If a subject has an adverse event with unknown relationship, then the subject will be counted in the relationship category of "unknown," even if the subject has another occurrence of the same event with a relationship present. The only exception is if the subject has another occurrence of the same adverse event with a relationship assessment of "Reasonable Possibility." In this case, the subject will be counted under the "Reasonable Possibility" category.

The number and percentage of subjects experiencing one or more adverse events in the following adverse event categories during the 12-week Treatment Period will be summarized by PT for overall treatment period interval and overall. The PTs will be presented by decreasing frequency overall.

- Any TEAE
- Any TEAE that was moderate or severe

A list of subject numbers associated with each PT will also be presented for all TEAEs.

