4.0 Study Objectives, Design and Procedures

4.1 Objectives

The primary objective of this interventional study is to examine the effect of LCIG treatment relative to that of Optimized Medical Treatment (OMT) on dyskinesia as measured by the Unified Dyskinesia Rating Scale (UDysRS) Total Score.

The Secondary objective is to assess the effect of LCIG treatment relative to that of OMT on dyskinesia as measured by PD Diaries, motor symptoms, motor complications, health-related outcome measures, safety and tolerability.

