4.3 Sample Size

Approximately 60 subjects will be enrolled into the study and randomized in a 1:1 ratio to either optimized medical treatment (OMT) or LCIG treatment. Subject randomization will be stratified by country. For sample size determination, it is assumed that the difference of improvement is 10 points on UDysRS total score between the LCIG treatment group and OMT group based on results reported by Pahwa et al (2015). The pooled standard deviation is assumed to be 12 based on results reported by Goetz et al (2013). Assuming that the treatment group difference is 10 points and the pooled standard deviation is 12, 27 subjects per group will have 85% power to declare statistical significance on the primary endpoint at a two-sided significance level of 0.050 based on calculations using nQuery + nTerim 4.0. It is further assumed that 10% of randomized subjects in either treatment group will not provide post-randomization efficacy assessment. Therefore the total planned enrollment is decided to be approximately 60 subjects.

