10.0 Safety Analysis

10.1 General Considerations

Unless noted otherwise, all safety analyses will be performed on the Safety Dataset. Treatment group differences in safety parameters are evaluated using two-sided test at the significance of 0.050.

Unless otherwise specified, treatment group differences in continuous safety variables (e.g., changes from baseline to final observation on laboratory test variables) will be assessed using an ANOVA model with the term of treatment, and the treatment group differences in binary safety variables will be evaluated using a Fisher's exact test.

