10.3.1 Analysis of Mean Changes for Laboratory Tests

Analyses of mean change from baseline to each planned visit and to the minimum, maximum and final value during the 12-week Treatment Period will be presented by treatment group for each continuous hematology, chemistry, urinalysis, and special laboratory variable.

For each change from baseline analysis, the following summary statistics for each treatment group will be presented: sample size, baseline mean, visit mean, and the mean, standard deviation, and median of the change from baseline. The baseline and visit means will be calculated for each visit for subjects who have both a baseline and visit value. The mean changes for the LCIG group and for the OMT group will be compared using an ANOVA with treatment as the factor. LS mean, standard error, 95% confidence interval and *P* value will be presented.

[figure not shown]
Analyses of mean change from baseline to each planned visit and to the minimum, maximum and final value during the Transition Period will be presented for each continuous special laboratory variable for LCIG subjects who enter the Transition Period.

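### Adverse-event incidence is compared between arms with no effect estimate or confidence interval, and P values above 0.100 are not printed, so the output does not show how large an excess risk on LCIG remains possible

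*SAP*

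**What the plan says.** SAP 4.1 makes the comparison with OMT on "motor symptoms, motor complications, health-related outcome measures, safety and tolerability" part of the secondary objective. SAP 10.1 sets the inferential rule: "Treatment group differences in safety parameters are evaluated using two-sided test at the significance of 0.050". It adds that treatment group "differences in binary safety variables will be evaluated using a Fisher's exact test", unless otherwise specified.

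SAP 10.2.2 applies this to three categories: any TEAE, any serious TEAE and any TEAE that led to discontinuation of study drug. The counts and percentages "will be summarized for each treatment group and for overall subjects by primary SOC and PT for overall treatment interval". Then: "The percentage of subjects in the LCIG group and in the OMT group will be compared using Fisher's exact test". The next sentence limits the display to P values not above "0.100 when rounded to three digits will be presented".

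Neither SAP 10.2 nor protocol 8.1.4 plans a risk difference, ratio or interval for adverse events. By contrast, SAP 10.3.1 asks for "LS mean, standard error, 95% confidence interval and" the P value when laboratory mean changes are compared. SAP 10.4.1 and 10.5.1 ask for the same for vital signs, weight and ECG. None of these three sections has a print limit.

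The design is small: "Approximately 60 subjects will be enrolled into the study and randomized in a 1:1 ratio" (SAP 4.3).

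**The concern.** The trial sets a possible benefit on dyskinesia against the risks of a drug, device and procedure combined. Adverse events carry most of that risk information, yet they are the one part of the between-arm safety comparison with no planned measure of effect or precision. When P exceeds 0.100 the inferential cell is empty. An empty cell looks the same whether the data exclude an important excess or are too sparse to say anything. At this sample size the second case is common for serious events, discontinuations and less frequent individual events. A reader of the planned tables would have the two percentages but no statement of what excess risk is still compatible with them.

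**Working it through.** **Inputs.** About 30 per arm (60 randomized 1:1, SAP 4.3). Two-sided Fisher test at 0.050 (SAP 10.1). P rounded to three decimals and printed if 0.100 or less (SAP 10.2.2). LCIG rates from the pivotal study: 56.8%, 51.4%, 29.7%, 21.6% and 18.9% for individual events (protocol 3.0). The documents give no OMT rates and no safety difference regarded as relevant, so OMT risks and all other LCIG risks below are assumptions.

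**The plan's own figure.** The only design calculation is for efficacy. For a 10-point difference, SD 12 and 27 per group, noncentral-t power is 0.852, which agrees with the stated 85%. Allowing for 10% loss, 54/0.9 = 60. The sample size reproduces. No power or precision is stated for safety.

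**Step 1: what counts trigger the rule at 30 v 30.** With no OMT events, 5 LCIG events are needed for P to be printed (P = 0.052) and 6 for significance (P = 0.024). With one OMT event, 7 are needed for printing and 8 for significance.

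**Step 2: how often the rule responds.** Let x and y be the LCIG and OMT event counts. The chance of significance is the sum, over all tables with P ≤ 0.050, of Bin(x; 30, p_LCIG) × Bin(y; 30, p_OMT). The chance of an unprinted P is the same sum over tables with P > 0.100.

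| OMT v LCIG risk | Significant | P not printed |
|---|---|---|
| 0% v 10% | 7% | 83% |
| 10% v 20% | 10% | 84% |
| 3% v 15% | 15% | 74% |
| 5% v 20% | 24% | 64% |
| 10% v 30% | 37% | 51% |
| 5% v 25% | 44% | 43% |
| 5% v 21.6% | 30% | 57% |
| 0% v 18.9% | 51% | 31% |
| 5% v 29.7% | 62% | 26% |
| 0% v 29.7% | 92% | 3% |
| 5% v 51.4% | 99% | 1% |
| 0% v 56.8% | 100% | 0% |

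**Step 3: what an unprinted result can hide.** Take 4/30 on LCIG against 0/30 on OMT. One tail is C(30,4)/C(60,4) = 27405/487635 = 0.0562. The arms are equal in size, so two-sided P = 0.112, which is not printed.

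Newcombe interval: the Wilson limits are 5.3% to 29.7% for 4/30 and 0% to 11.4% for 0/30. The difference is 13.3 points.
- Lower limit: 0.133 − √[(0.133 − 0.053)² + (0.114 − 0)²] = −0.006.
- Upper limit: 0.133 + √[(0.297 − 0.133)² + 0²] = 0.297.

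The interval is −1 to +30 points. Other unprinted tables look similar: 3 v 0 (P = 0.237) gives −3 to +26 points, 6 v 1 (P = 0.103) gives 0 to +34, and 7 v 2 (P = 0.145) gives −2 to +35.

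**Step 4: sensitivity to arm size.** The safety dataset keeps all OMT subjects but only those LCIG subjects who had a tube placement procedure (SAP 5.0). Suppose three LCIG subjects never do, so the comparison is 27 v 30. The same 4 v 0 events then have tail C(27,4)/C(57,4) = 17550/395010 = 0.044. The opposite tail, 27405/395010 = 0.069, is larger and is not added. P moves from 0.112 and unprinted to 0.044 and significant. The Newcombe interval moves only from (−1, +30) to (0, +32) points.

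**The case against.** The strongest reply is that this is a display choice. Counts and percentages by arm are always tabulated, with severity, relationship, special-interest and subgroup summaries and listings (SAP 10.2.1 to 10.2.5). In the example a reader sees 0% against 13.3%, and can compute the difference and an interval from the printed counts. Suppressing large P values may also curb over-reading across many SOC and preferred-term rows. Low power for uncommon events is inherent in a 60-subject trial sized for efficacy, and an interval describes that imprecision without curing it. All of this stands, and it limits the point to reporting.

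Three stronger readings are tempting and are not supported:
- A reader might infer that adverse-event safety is judged by the Fisher test alone. The always-printed descriptive tables contradict that. The test is only the sole between-arm inference.
- A reader might infer that the plan treats an unprinted P as showing no difference. Neither document gives such a rule, a safety margin or a similarity claim. They also give no caution against that reading.
- A reader might infer that most relevant harms would be missed. The leading procedural harms, at about 30% or more on LCIG against near 0% on OMT, have 92% to 100% power.

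The print limit also follows the three categories in SAP 10.2.2. It is not repeated for the events of special interest in 10.2.3, which fall under the general Fisher rule in 10.1. Those comparisons have no interval either. Weight change itself does get a 95% interval, under 10.4.1.

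**Conclusion.** The point holds as a reporting weakness. For any, serious and discontinuation TEAEs the only planned between-arm inference is a 0.050 Fisher test with P hidden above 0.100, and no adverse-event comparison has an effect estimate or interval. For differences of about 10 to 20 points in low-to-moderate-frequency events, at OMT risks of 3% to 10%, power is 10% to 44% and P goes unprinted in 43% to 84% of trials. Unprinted results can leave excess risks of about 26 to 35 points open. The rule does better when the OMT risk is essentially zero and the LCIG risk approaches 20% (0% v 18.9%: 51% significant, 31% unprinted).

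These figures assume 30 per arm and the stated event risks, since the documents supply no OMT rates. The primary analysis, its error control and the sample size are unaffected. The change is worth making because the comparative safety objective is stated and the better presentation is almost free.

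**What to change.** - **SAP 10.2.2:** for the overall rows of any TEAE, any serious TEAE and any TEAE leading to discontinuation, delete the limit that prints P only at 0.100 or less. Present the LCIG-minus-OMT risk difference with a 95% confidence interval (Newcombe or Miettinen-Nurminen) whatever the P value.
- **SAP 10.2.3:** add the same risk difference and interval for the polyneuropathy and weight-loss events of special interest. The gastrointestinal summary is planned for LCIG only and needs no contrast.
- **SAP 10.1:** state that a non-significant or unprinted P is not evidence of similar safety.
- SOC and preferred-term rows can stay descriptive.

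The cost is SAP wording and one extra column in five summary rows, with no new data, visits or subjects. The small downside is that wide intervals will make the safety comparison look less reassuring.

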6.4 Relationship to Study Drug

For the assessment of drug event relationship, LCIG should be considered a therapeutic system consisting of drug, devices and placement procedure. Causality assessments are always made over the system as a whole.

For the assessment of drug event relationship, those randomized to OMT should evaluate relatedness to any of the subject's anti-PD medication.

The Investigator will use the following definitions to assess the relationship of the adverse event to the use of study drug:

Reasonable Possibility	An adverse event where there is evidence to suggest a causal relationship between the study drug and the adverse event.
No Reasonable Possibility	An adverse event where there is no evidence to suggest a causal relationship between the study drug and the adverse event.

For causality assessments, events assessed as having a reasonable possibility of being related to the study drug will be considered "associated." Events assessed as having no reasonable possibility of being related to study drug will be considered "not associated." In addition, if the Investigator has not reported causality or deemed it not assessable, AbbVie will consider the event associated.

If an Investigator's opinion of no reasonable possibility of being related to study drug is given, an 'Other' cause of event must be provided by the Investigator for the serious adverse event.

6.5 **Adverse Event Collection Period**

[figure not shown]
Protocol-related non-serious adverse events that occur after signing the informed consent, prior to the start of study drug administration, will be collected. All adverse events reported from the time of randomization until 30 days following last OMT dose, last study visit, discontinuation of study drug administration and removal of the PEG-J tube or last LCIG Commercial Transition Visit have elapsed will be collected, whether solicited or

spontaneously reported by the subject. In addition, serious adverse events will be collected from the time the subject signed the study-specific informed consent.

Adverse event information will be collected as shown in Figure 3.

Figure 3. **Adverse Event Collection**

6.6 **Adverse Event Reporting**

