Unless otherwise specified, the treatment group differences in continuous safety variables (e.g., change from baseline to final observation on laboratory tests) will be assessed using an ANOVA model with the term of treatment, and the treatment group differences in binary safety variables will be evaluated using Fisher's exact test.

8.1.4.1 **OMT and LCIG Treatment Exposure**

The duration of OMT exposure will be calculated for each subject as the date of the last visit minus the date of randomization. The duration of LCIG study drug exposure will be calculated for each subject as the date of the last dose of LCIG study drug minus the date of the first dose of LCIG study drug plus 1. The duration of LCIG device exposure will be calculated for each subject as the date of the last study tube exposure minus the date of the first study tube placement procedure plus 1. For subjects with all study tubes removed on or after the last day of LCIG study drug infusion, the date of last study tube exposure will be the last tube removal date. For all other subjects randomized to LCIG treatment, the date of last study tube exposure will be the day of the final visit. The duration of OMT and LCIG study drug exposure and LCIG device exposure will be summarized with descriptive statistics (number of subjects with non-missing data, mean, and standard deviation, median, minimum and maximum).

8.1.4.2 **Adverse Events**

Adverse events will be coded using the most current version of the Medical Dictionary for Regulatory Activities (MedDRA). Adverse events will be summarized by primary MedDRA system organ class (SOC) and preferred term (PT). Subjects reporting more

than one adverse event for a given MedDRA PT will be counted only once for that term. Subjects reporting more than one adverse event within an SOC will be counted only once for the SOC total. Subjects reporting more than one adverse event will be counted only once in the overall adverse event total.

Each adverse event will be categorized by severity (mild, moderate, severe) and by relationship to study treatment (reasonable possibility, or no reasonable possibility). Detailed search criteria for adverse events of special interest (AESIs) will be defined in an SAP prior to database lock.

A treatment-emergent adverse event (TEAE) is defined as any adverse event with onset during the treatment period or within 30 days of the end of the treatment period:

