12.0 Summary of Changes

This SAP contains no change in analysis from the latest version of the protocol (Protocol Amendment 1).

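### No planned table applies the protocol rule that adverse events without a causality rating count as associated, and the 12-week related-TEAE overview row names LCIG only

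*SAP*

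**What the plan says.** **Missing causality.** Protocol 6.4 makes *associated* the class for events rated a reasonable possibility, and adds that "if the Investigator has not reported causality or deemed it not assessable, AbbVie will consider the event associated". Protocol 8.1.4.2 then categorises each adverse event "by relationship to study treatment (reasonable possibility, or no reasonable possibility", which leaves no third class. SAP 10.2.2 tabulates TEAEs by "maximum relationship category (reasonable possibility, no reasonable possibility, or unknown), as assessed by the investigator". Its rule for unrated events reads "If a subject has an adverse event with unknown relationship, then the subject will be counted in the relationship category of" *unknown*, and this applies even when another occurrence of the same event has a rating. The one exception is an occurrence rated a reasonable possibility.

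**Reference treatment.** For subjects in the comparator arm, Protocol 6.4 says that "those randomized to OMT should evaluate relatedness to any of the subject's anti-PD medication". The SAP 10.2.1 overview has one relatedness row for the 12-week Treatment Period: "Any TEAE that was rated by the investigator as having a reasonable possibility of relationship to levodopa-carbidopa intestinal gel". The same row is repeated for the Transition Period.

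**Declared departures.** SAP 12.0 states: "This SAP contains no change in analysis from the latest version of the protocol".

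**The concern.** The protocol has a conservative rule for a missing causality rating, and the SAP has no step that carries it out. An unrated event cannot enter the overview row, which requires an investigator rating, and in the 10.2.2 table it sits outside the related category. If ratings are missing, the reported number of subjects with a related TEAE is lower than the protocol rule would give, and SAP 12.0 does not tell the reader so.

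The second problem concerns what the 12-week overview row measures in the OMT arm. OMT subjects receive no LCIG, and their causality ratings refer to other drugs. A row defined by relationship to LCIG has no meaningful count for them. At stake is one headline safety figure, the related-TEAE rate, and any comparison of that figure between arms.

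**Working it through.** The plan gives no figure to reproduce here. The check sets the texts side by side and then sizes the effect.

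**1. One preferred term in one LCIG subject who has no other related event**

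| Ratings recorded | Protocol 6.4 and 8.1.4.2 | SAP 10.2.2 | SAP 10.2.1 row |
|---|---|---|---|
| Unrated only | Reasonable possibility | Unknown | Not counted |
| Unrated, and no reasonable possibility | Reasonable possibility | Unknown | Not counted |
| Unrated, and reasonable possibility | Reasonable possibility | Reasonable possibility | Counted |
| No reasonable possibility only | No reasonable possibility | No reasonable possibility | Not counted |

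The documents differ in the first two lines only. In those lines the SAP never classes the subject as unrelated, but it does not class the subject as related either.

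**2. Is the protocol rule applied elsewhere in the SAP?** Relationship appears in the overview lists of 10.2.1 and in the maximum-relationship table of 10.2.2. Neither moves *unknown* to associated, and no other planned table deals with relationship.

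**3. The OMT arm in the 12-week overview row**

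- SAP 5.0 puts all subjects randomized to OMT in the Safety Dataset, and SAP 10.1 applies that dataset to all safety analyses unless noted otherwise.
- SAP 10.2.1 does not limit the row to one arm. Where the SAP intends such a limit it says so, as for GI events in 10.2.3.
- Protocol 5.5.3 allows study drug to be dispensed only to subjects randomized to LCIG.

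Two readings follow. Read literally, no OMT event can be related to LCIG and the OMT cell is a structural zero. If the programmer instead enters the OMT ratings made against anti-PD medication, the count is meaningful but the label is wrong.

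**4. Size of the missing-rating effect**

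Inputs: about 60 subjects randomized 1:1 (SAP 4.3), so about 30 per arm. The number k of subjects moved by the rule is not given in the documents and is an assumption here.

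Shift in an arm's related rate = 100 × k / N percentage points.

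| k | N = 30 | N = 27 |
|---|---|---|
| 0 | 0 | 0 |
| 1 | 3.3 | 3.7 |
| 2 | 6.7 | 7.4 |
| 3 | 10.0 | 11.1 |

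N = 27 is the evaluable number per group in SAP 4.3 and shows the effect of a smaller denominator.

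**5. Illustration of the structural zero**

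SAP 10.1 makes Fisher's exact test the default for binary safety variables. SAP 10.2.1 does not say whether it is used on the overview. If it were, with 30 per arm and none in OMT, the two-sided p-value for x related subjects in LCIG would be 2 × C(30,x) / C(60,x):

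- x = 5: 2 × 142,506 / 5,461,512 = 0.052
- x = 6: 2 × 593,775 / 50,063,860 = 0.024

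The counts are invented for illustration. On the literal reading, these results would be the same whatever OMT-related events had occurred.

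**The case against.** The strongest defence of the SAP has five parts.

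- **The 10.2.2 table is labelled as the investigator's assessment, while Protocol 6.4 describes what the sponsor will consider.** Showing raw ratings with a visible *unknown* column is legitimate, and a reader can add that column to the related one. Ranking *unknown* above *no reasonable possibility* is also cautious. This stands, so a reader who infers that the SAP reverses the protocol goes too far: unrated events are never merged into unrelated. What remains is that no table applies the sponsor rule and the third category is not declared.
- **The protocol's own list in 8.1.4.2 asks for TEAEs by maximum relationship, and SAP 10.2.2 supplies that by treatment group without naming a drug.** This stands. A reader might infer that OMT causality data are lost from the analysis. They are at risk only in one overview row.
- **The LCIG label is probably an unadapted template.** This may be so. The documents do not establish that the OMT cell would be programmed as zero, so 0/30 cannot be called a certainty. The alternative is still a mislabelled row.
- **Missing ratings should be rare, because Protocol 6.1 has the investigator record relationship for each event.** This stands, and the effect may be nil.
- **Rewording would not make the arms comparable.** This stands too. Protocol 6.4 judges LCIG causality over drug, devices and placement procedure together, but OMT causality over medication only.

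The LCIG wording does no harm in the Transition Period list, because only LCIG subjects enter that period.

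**Conclusion.** The mismatch is real and is in current text. The protocol's rule for missing or not-assessable causality is applied in no planned table, the SAP uses three relationship categories where the protocol uses two, and SAP 12.0 declares no change. If any ratings are missing, the related-TEAE count is understated relative to the protocol rule, by 3.3 percentage points per affected subject at 30 per arm. The *unknown* column of the 10.2.2 table would show such subjects.

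The 12-week overview row is also wrong as worded for OMT: a structural zero if read literally, a wrong label otherwise.

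A reader might conclude that the related-TEAE figure is wrong in both arms. The documents do not support that. Understatement depends on missing ratings, whose number is not given, and the OMT zero depends on a literal reading. The by-arm table in 10.2.2 can still report OMT ratings.

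The point concerns safety reporting only. Efficacy and the total, serious and discontinuation TEAE counts are untouched. The correction is worth making before database lock because it is cheap and affects a reported safety number.

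**What to change.** 1. **SAP 10.2.1, 12-week overview row.** Reword to: *reasonable possibility of relationship to assigned treatment (LCIG system, or any anti-PD medication for OMT)*. Count missing or not-assessable causality as reasonable possibility in this row, and footnote the number of subjects so classified in each arm. The wording of the Transition Period row can stay.
2. **SAP 10.2.2, relationship table.** Choose one option. Either apply the same rule and drop the investigator-assessed label, or keep the investigator-rated table with its *unknown* column and add a line that applies the Protocol 6.4 rule. The second option keeps the raw ratings visible.
3. **Note under both tables.** State that LCIG causality covers drug, device and procedure while OMT causality covers medication only, so related rates are not directly comparable between arms.

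The cost is SAP wording and one derivation rule, with no new data. The downside is that related counts may rise slightly.
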